1 SUMMARY OF TRIAL PROTOCOL

1.1 HYPOTHESIS

The NutriVax-Measles study will test the hypothesis that a SQ-LNS supplementation program coupled with a standard Expanded Program on Immunization (EPI) in health facilities for children aged 6-23 months (NutriVax program) could increase vaccination coverage, particularly measles, after twelve months of implementation. NutriVax-Measles will also assess the barriers, facilitators and cost of NutriVax plus EPI compared to EPI alone in children aged 6-23 months. Thanks to NutriVax-Measles study, we will be able to see if SQ-LNS as an incentive for immunizations leads to cost-efficient benefits compared to EPI alone. Thus, it will build evidence about whether it is possible to achieve a double impact on increased vaccination coverage and improved malnutrition indicators.

1.2 Study objectives and endpoints

1.2.1 Objectives

Primary objective:

To estimate the effectiveness of a SQ-LNS mass supplementation program added to routine immunization program compared to routine immunization program alone in terms of measles vaccine coverage, after 12 months of program implementation, in children aged 12-23 months in the endline cross-sectional household survey.

Main secondary objective:

To estimate the effectiveness of a SQ-LNS mass supplementation program added to routine immunization program compared to routine immunization program alone in terms of measles vaccine coverage, after 12 months of program implementation, in children aged 6-12 months at inclusion in the longitudinal follow-up survey.

Secondary objectives:

- To estimate the effectiveness of a SQ-LNS mass supplementation program added to routine immunization program compared to routine immunization program alone in children aged 6-23 months, after 12 months of program implementation, in terms of 1) all other infant vaccines uptake, 2) timeliness of age-eligible vaccinations; 3) anthropometric status, 4) uptake of pediatric curative and preventive health consultations and activities.
- To assess the barriers and facilitators to SQ-LNS mass supplementation implemented as part of a routine immunization program in health facilities, from the perspectives of parents/legal guardian of children aged 6-23 months, health care providers, community health workers and community representatives.
- To assess the cost-efficiency of a SQ-LNS mass supplementation program versus routine immunization program in terms of cost per child supplemented and vaccinated.

1.2.2 Endpoints

The primary endpoint is the measles vaccine coverage, defined as the proportion of children aged 12-23 months in the endline survey who have received at least one dose of measles vaccine, as reported on their vaccination card.

The main secondary endpoint is the measles vaccine coverage, defined as the proportion of children aged 6-12 months at inclusion in the longitudinal follow-up survey, who have received at least one additional dose of measles vaccine, as reported on their vaccination card, administered between inclusion and the end of follow-up.

Secondary endpoints:

- Proportion of children with at least one measles vaccines as reported on their vaccination card or by recall.
- Timeliness of measles 1 vaccination (i.e. within 30 days of turning 9 months), as reported on their vaccination card.
- Timeliness of measles 2 vaccination (i.e. within 30 days of turning 15 months), as reported on their vaccination card.
- Proportion of children with each of the following vaccine doses, as reported on their vaccination card or by recall: measles 1, measles 2, pentavalent 1 and 3, yellow fever and meningitis.
- Proportion of children with age-eligible vaccines such as measles 1, measles 2, yellow fever, meningitis, and catch-up vaccines like pentavalent 1 and 3, as reported on a vaccination card or by recall.
- Proportion of zero-dose children as reported on a vaccination card or by recall, two definitions : none dose, and no penta 1 dose.
- Proportion of fully immunized children, i.e. children who received all age-eligible vaccination.
- Anthropometric parameters mean change in children: MUAC, z scores for MUAC for age, weight for age, weight for height, and height for age.
- Proportion of vitamin A dose 1 given at 6 months and dose 2 given at 12 months
- Evolution of aggregate data collected routinely at health facilities, mean and proportion: paediatric curative and preventive consultations, vaccination activities, SQ-LNS activities, activities on vaccination and Infant and Young Child Feeding (IYCF) sensitization, vaccine and SQ-LNS consumption.
- Barriers and facilitators to access health care centres and receive SQ-LNS mass supplementation implemented as a routine preventive program nested in health facilities activities.
- Adherence to SQ-LNS supplementation.
- Barriers and facilitators to vaccination uptake at health facilities activities.
- Cost per child vaccinated and supplemented compared to cost per child vaccinated only, using a facility and caregiver perspective (see 5.1.4 Cost-efficiency survey section for precision) to identify all provider and caregiver costs associated with treatment.

Table 1: Primary and secondary endpoints (vaccination coverage and anthropometric parameter) in the NutriVax-Measles study

Endpoints	Measurement variable	Denominator and data collection mode	Method of aggregation	Timepoint
Primary				
Measles vaccine coverage	At least one dose of measles vaccine reported on vaccination card	Children aged 12-23 months in the cross-sectional endline survey	Proportion	After one year of the SQ-LNS program (measured in the endline HHS)
Main secondary				
Measles vaccine coverage	At least one additional dose of measles vaccine reported on vaccination card administered between inclusion and the end of follow-up	Children aged 6-12 months at inclusion in the longitudinal follow-up survey	Time-to-event analysis; cumulative incidence at end of follow-up	Between inclusion and the end of longitudinal follow-up
Secondary				
Measles vaccine coverage	At least one measles vaccine as reported on a vaccination card or by recall	Children aged 12-23 months in the cross-sectional endline survey	Proportion	After one year of the SQ-LNS program (measured in the endline HHS)
	At least one additional dose of measles vaccine reported on vaccination card or by recall, administered between inclusion and the end of follow-up	Children aged 6-12 months at inclusion in the longitudinal follow-up survey	Time-to-event analysis; cumulative incidence at end of follow-up	Between inclusion and the end of longitudinal follow-up
	Measles 2 vaccine as reported on a vaccination card or by recall	Children aged 12-23 months in the cross-sectional endline survey	Proportion	After one year of the SQ-LNS program (measured in the endline HHS)
		Children aged 6-12 months at inclusion in the longitudinal follow-up survey	Time-to-event analysis; cumulative incidence at end of follow-up	Between inclusion and the end of longitudinal follow-up
Timeliness of measles 1 vaccination.	Measles 1 vaccine received within 30 days of turning 9 months by card	Children aged 12-23 months in the cross-sectional endline survey	Proportion	After one year of the SQ-LNS program (measured in the endline HHS)
	Measles 1 vaccine received within 30 days of turning 9 months by card or by recall	Children aged 6-12 months at inclusion in the longitudinal follow-up survey	Time-to-event analysis; cumulative incidence at end of follow-up	Between inclusion and the end of longitudinal follow-up
Timeliness of measles 2 vaccination.	Measles 2 vaccine received within 30 days of turning 15 months by card or by recall	Children aged 12-23 months in the cross-sectional endline survey	Proportion	After one year of the SQ-LNS program (measured in the endline HHS)
	Measles 2 vaccine received within 30 days of turning 15 months by card or by recall	Children aged 6-12 months at inclusion in the longitudinal follow-up survey	Time-to-event analysis; cumulative incidence at end of follow-up	Between inclusion and the end of longitudinal follow-up

Other infant vaccines coverage	Pentavalent 1 and 3, yellow fever, and meningitis vaccine by vaccination card or by recall	Children aged 12-23 months in the cross-sectional endline survey	Proportion	After one year of the SQ-LNS program (measured in the endline HHS)
		Children aged 6-12 months at inclusion in the longitudinal follow-up survey	Time-to-event analysis; cumulative incidence at end of follow-up	Between inclusion and the end of longitudinal follow-up
Additional infant vaccines coverage	Catch-up pentavalent 1 and 3, and age-eligible yellow fever, meningitis, by vaccination card or by recall	Children aged 6-12 months at inclusion in the longitudinal follow-up survey	Time-to-event analysis; cumulative incidence at end of follow-up	Between inclusion and the end of longitudinal follow-up
Zero-dose	No measles + pentavalent + yellow fever + meningitis vaccines reported by vaccination card or by recall	Children aged 12-23 months in the cross-sectional endline survey	Proportion	After one year of the SQ-LNS program (measured in the endline HHS)
		Children aged 6-12 months at inclusion in the longitudinal follow-up survey	Time-to-event analysis; cumulative incidence at end of follow-up	Between inclusion and the end of longitudinal follow-up
	No pentavalent 1 vaccine reported by vaccination card or by recall	Children aged 12-23 months in the cross-sectional endline survey	Proportion	After one year of the SQ-LNS program (measured in the endline HHS)
		Children aged 6-12 months at inclusion in the longitudinal follow-up survey	Time-to-event analysis; cumulative incidence at end of follow-up	Between inclusion and the end of longitudinal follow-up
Proportion of children fully immunized	Children who had received all childhood vaccinations recommended by the Nigeria MOH, by vaccination card or by recall.	Children aged 12-23 months in the cross-sectional endline survey	Proportion	After one year of the SQ-LNS program (measured in the endline HHS)
		Children aged 6-12 months at inclusion in the longitudinal follow-up survey	Time-to-event analysis; cumulative incidence at end of follow-up	Between inclusion and the end of longitudinal follow-up
Anthropometric parameters	MUAC, z scores for MUAC for age, weight for age, weight for height, and height for age	Children aged 6-12 months at inclusion in the longitudinal follow-up survey	Median/mean	End of follow-up
Vitamin A supplementation coverage	Dose 1 given at 6 month and dose 2 given at 12 months by vaccination card or by recall	Children aged 12-23 months in the cross-sectional endline survey	Proportion	After one year of the SQ-LNS program (measured in the endline HHS)
		Children aged 6-12 months at inclusion in the longitudinal follow-up survey	Time-to-event analysis; cumulative incidence at end of follow-up	Between inclusion and the end of longitudinal follow-up

1.3 Study design

This NutriVax-Measles study will consist in conducting a pragmatic parallel cluster randomized trial (PCT) with baseline measure with different populations and data collection modes: 1) a baseline and an endline cross-sectional household surveys (HHS) of children aged 12-23 months, 2) a longitudinal 12 months follow-up household survey (LS) of children aged 6-12 months at inclusion, 3) two cross-sectional Qualitative Feasibility and Acceptability Survey (QFAS) of parents/legal guardian of children aged 6-23 months, health care providers, community health workers, 4) caregiver cost survey (CCS) of the caregivers of children from the longitudinal cohort (population 2), and 5) a health facility cost survey of a randomized sub-sample of health facilities.

Thanks to these different data collection modes, measles vaccination coverage and the quantitative secondary endpoints will be measured both at the community level using the endline HHS and at the individual level using the LS (Figure 1).

The NutriVax program will be assessed within a routine program implemented at scale. PCT pragmatic studies are designed to guide decision-making in the real-world clinical practice and policy settings while maintaining the strengths of individual randomized controlled trials if they are systematically designed and performed properly. The pragmatic attitude increases external validity to ensure that the results can be generalized in everyday practice in this context and other similar settings^{2,3}.

The unit of randomization (i.e. cluster) will be a ward and its catchment area. We will include exhaustively all wards of each LGA where the study will take place.

[figure not shown]

Figure 1. Study design chart.

1.4 Study population

1.4.1 Eligibility criteria

- Baseline and endline household surveys

Inclusion criteria

- Aged 12-23 months;
- With oral informed consent of parent or legal guardian;
- Residing in the catchment settlements of wards included in the study.

Exclusion criteria

- Already included in the longitudinal follow-up.

- Longitudinal follow-up survey

Inclusion criteria

- Aged 6-12 months;
- With written informed consent of parent or legal guardian;
- Residing in the catchment settlements of wards included in the study.

Exclusion criteria

- Acute malnutrition criteria as per the WHO definition (i.e. MUAC<125 or WHZ < -2 or nutritional edema). Such children will be referred for treatment;
- Known medical complication that requires referral for hospitalization;
- Known allergies to SQ-LNS or SQ-LNS contraindication;
- Any other condition interfering with protocol adherence or the ability to give informed consent, in the judgment of the Field Investigator

For instance, medical, occupational or other conditions of the participant or parent/guardian may make routine home visits and evaluation difficult or make the child a poor candidate for retention. Any such potential exclusion must be validated by the Field Investigator.

1.4.2 Sampling methods

Both HHS and longitudinal follow-up surveys will be carried out at community level. Household and participants will be selected through a multi-stage sampling method. We will follow the WHO reference manual for vaccination coverage cluster surveys⁴. The sampling will be carried out in three stages in each randomized cluster (which will be a ward), namely: (1) random selection of 'settlement' in each cluster using probability proportional to size (PPS) method; (2) systematic random selection of households in each settlement with equal probability using population estimation used by the MoH for the planification of health activities; (3) selection

of the youngest eligible child in the household, and random selection of one among the eligible child guardians (Figure 2).

We will use the following definition to identify a household: “A person or a group of persons, related or unrelated, who live together and share a common source of food and livelihood, and recognize one person as a head.”, as per the usual definition used in population survey in Nigeria (26).

A specific and detailed standardized operation procedure for the sampling process will be developed prior to the baseline HHS and the LS inclusion.

[figure not shown]

Figure 2 : Sampling survey using 3-stage random sampling method

The same sampling methods will be used for the inclusion of children in the HHS and for the inclusion of children in the LS.

1.5 Study interventions

The NutriVax-Measles study will compare two interventions randomly assigned to either:

1) The standard Expanded Program on Immunization (EPI) in children aged 6-23 months delivered according to the Ministry of Health’s routine plans in the community and at health centres (i.e. PHCCs) and health posts, named the standard EPI arm,

2) The NutriVax program combining the EPI in children aged 6-23 months according to the Ministry of Health’s routine plans in the community and at health centres (i.e. PHCCs) and health posts associated with SQ-LNS mass supplementation integrated into pre-existing services delivered at health centres (i.e. PHCCs) for children 6-23 months of age, named the NutriVax arm.

1.6 Study sites

Research and operational activities will take place at community level and in the 20 PHCCs of the 2 LGAs of Karasuwa and Nguru LGAs. Each LGA has 10 wards and there is one PHCC per ward.

1.7 Randomisation

The unit of randomization (cluster) will be the ward and its catchment area.

Randomization will be stratified by LGA in order to promote balance of the intervention among both LGAs and to give the same opportunity to receive the intervention in both LGAs. Also, the two LGAs may have different populations or contexts that could be a potential confounding factor.

Randomization will be done prior to the baseline survey, because of logistical constraints required for preparing SQ-LNS distribution at health centres (PHCCs), but kept concealed to the data collector until the completion of the baseline survey. After baseline survey completion, the study will be open, as it will not be possible to blind participants or study staff to SQ-LNS supplementation.

In each LGA, the 10 wards will be randomized the same day, by lottery from an envelope, in presence of PHCC department, local community representatives and held in the local language (Hausa). Clusters will be randomly allocated at a ratio of 1:1 either to the standard EPI arm or to the NutriVax arm.

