3.3 BASELINE RESULTS DESCRIPTION

At the end of the HHS baseline cross-sectional survey, all primary and secondary endpoints will be described at cluster level.

Individual characteristics will be described between arms to assess for sample representativity and possibly identify imbalances. Since the allocation of clusters between arms is carried out randomly, it is known that any differences that do occur must have occurred by chance. This means that the null hypothesis is known to be true, so there is no logic in testing it. The point of displaying between-arm comparisons is not to carry out a significance test, but to describe in quantitative terms how large any differences were.^{9(p200)}

We will use the findings of the baseline analysis to decide which variables need to be adjusted for in the final analysis.

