3.4.2.1 Description

We will describe at each visit, globally and by age classes at inclusion ([6-9[months, [9-12] months):

- proportion of measles vaccine dose 1,
- proportion of measles vaccine dose 2,
- proportion of patients of at least one additional dose of measles vaccine.

For children included at [6-9[months old, measles vaccine dose 1 is supposed to be administered before the first follow-up visit (i.e V1) occurring 4 months after inclusion (i.e M4); measles vaccine dose 2 is supposed to be administered before V2 (M8) if included at [7-9[months old or before V3 (M12) if included at [6-7[months old.

For children included at [9-12] months old, measles vaccine dose 1 is supposed to be administered before inclusion, and measles vaccine dose 2 is supposed to be administered before V1 (M4) if included at [11-12] months old or before V2 (M8) if included at [9-11[months old.

3.4.2.2 Main analysis first intention:

In first intention, analysis will be conducted at the individual level, adjusting for clustering.

A time-to-event approach will be used, where time is defined from inclusion to the first occurrence of an additional dose of measles vaccine. A shared frailty model (Cox proportional hazards model with a random intercept for cluster)^{16,17} will be used to estimate the effect of the intervention.

The intervention effect will be estimated as a hazard ratio (HR) with 95% confidence intervals, comparing the instantaneous risk of receiving an additional dose of measles vaccine between the intervention and control arm, accounting for clustering via the shared frailty term.

For interpretability, the cumulative incidence of vaccination at 12 months will be estimated from the shared frailty Cox model and reported by study arm, together with the absolute difference between arms. Kaplan–Meier curves will be used for descriptive visualization only.

This approach appropriately accounts for clustering, the timing of vaccination, and censoring, and provides a statistically valid and clinically interpretable estimate of the intervention effect.

No adjustment for baseline vaccination status is planned, as the expected number of doses depends on age at inclusion (for children aged 6–9 months at inclusion, 0 dose is expected).

The variance of the shared frailty term will be reported to describe the between-cluster variability.

Adjusted analyses

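### The main longitudinal model omits age and prior measles doses, although children are enrolled after a witnessed ward lottery and arm differences among them cannot be assumed to be chance only

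*SAP*

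**What the plan says.** **Order of events (section 1.7).** "Randomization will be done prior to the baseline survey, because of logistical constraints required for preparing SQ-LNS distribution". The wards of each LGA are drawn by lottery, with the PHCC department and community representatives attending. The result is "but kept concealed to the data collector until the completion of the baseline survey". Then: "After baseline survey completion, the study will be open".

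**Entry to the LS (section 1.4.1).** A parent or guardian gives written consent. One exclusion rests on judgement and covers circumstances that make home visits difficult or "make the child a poor candidate for retention. Any such potential exclusion must be validated by the Field Investigator". Section 1.4.2 adds random selection of households and takes the youngest eligible child. The SAP gives no dates for LS inclusion.

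**Baseline differences (section 3.3).** In describing individual characteristics by arm, the SAP reasons that, because wards were randomised, "it is known that any differences that do occur must have occurred by chance".

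**Main LS analysis (section 3.4.2.2).** This is a Cox model for time to the first additional measles dose, with arm and a ward frailty. It states: "No adjustment for baseline vaccination status is planned, as the expected number of doses depends on age at inclusion". A separate adjusted re-run lists age at inclusion, mother's age, study level, number of children, distance to the facility, food insecurity and two ward-level supply variables. It may also add variables suggested by the qualitative survey. Doses held at inclusion are not named.

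**The concern.** Randomising wards makes differences between wards a matter of chance. It does not do so for children who are consented or excluded after the draw, if anyone involved in those decisions knows the ward's arm. Willingness to consent and expected retention are plausibly related to a family's use of vaccination services. If they also differed by arm, the hazard ratio and the 12-month difference for the main secondary endpoint would mix enrolment selection with the programme effect.

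The main model makes no allowance for this, although the two most obvious baseline predictors of the event are already recorded. The reason given for leaving them out points the other way. If the number of doses a child should hold depends on age, then age and doses held, taken together, say what the child is still due.

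**Working it through.** **1. What the SAP settles about concealment**

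| Question | SAP |
|---|---|
| Allocation before enrolment of children? | Yes (1.7) |
| Who is kept unaware? | The data collector (1.7) |
| Until when? | End of the baseline survey (1.7) |
| Parents, health-centre staff, Field Investigator? | Not stated |
| Dates of LS inclusion? | Not stated |

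If LS inclusion ran alongside the baseline survey, data collectors were unaware, and the remaining routes are families and the Field Investigator. If it ran later, entry was open. Random household selection and the youngest-child rule limit the choice of child, but not refusal or discretionary exclusion.

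**2. Why age and prior dose matter to this event**

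Section 3.4.2.1 expects a child included at 6 to under 9 months to receive dose 1 before the month-4 visit. A child included at 9 to 12 months should already hold dose 1 and be due dose 2. The same event is thus a different dose, due at a different time since inclusion, according to age and doses held. The re-run justifies its age term by differing eligibility at baseline, which applies equally to the main model.

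**3. The plan's own LS sample size (section 1.8.2)**

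Inputs: 30% against 40%, two-sided 5%, 80% power, ICC 0.2, individual autocorrelation 0.5, 10 wards per arm, 5% unusable data. The cluster autocorrelation is not stated; 1 is assumed.

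- Individually randomised n per arm, unpooled: 353.2.
- With m = 28 per ward: 1 + 27 × 0.2 = 6.4.
- Baseline correlation: r = (28 × 0.2 + 0.8 × 0.5)/6.4 = 0.9375.
- Design effect: 6.4 × (1 − 0.9375²) = 0.775.
- Required per arm: 353.2 × 0.775 = 273.7, within 10 × 28 = 280.
- 28/0.95 = 29.5, so 30 per ward and 600 in total, as stated.

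The figure reproduces only with a baseline measure in the calculation. The main model uses none.

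**4. Possible size of selection (assumed rates)**

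Take 30% as incidence in both arms with no true effect. The 30% is the plan's baseline coverage, used as a stand-in for LS incidence. If one arm omits a fraction f of children whose incidence is q, its incidence becomes (0.30 − f·q)/(1 − f). The HR is approximated by ln(1 − p_new)/ln(0.70).

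| f | q | p_new | False difference | HR |
|---|---|---|---|---|
| 0.10 | 0 | 33.3% | +3.3 points | 1.14 |
| 0.10 | 0.10 | 32.2% | +2.2 points | 1.09 |
| 0.15 | 0 | 35.3% | +5.3 points | 1.22 |
| 0.15 | 0.10 | 33.5% | +3.5 points | 1.15 |

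A second illustration supposes that half of control children come from engaged families. The false difference is the arm difference in engaged share times the uptake gap:

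- Uptake 40% against 20%, shares differing by 5, 10 or 20 points: 1, 2 or 4 points.
- Uptake 50% against 10%, same shares: 2, 4 or 8 points.

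**5. Age mix alone (assumed rates)**

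If incidence is 45% in the younger class and 25% in the older, a 10-point shift in age mix moves the arm difference by 0.10 × (0.45 − 0.25) = 2 points.

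**The case against.** Several points on the other side stand.

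- **Section 3.3.** A reader might infer that the SAP tells the analyst to disregard imbalance. It does not. The section opens with the baseline household survey, argues only against significance testing, asks how large differences are, and uses the findings to choose adjustment variables. What remains is that its premise is worded for individual characteristics and that no different view is given for the LS.
- **Who knew.** A reader might infer that parents and the Field Investigator knew the allocation. That rests on silence. Section 1.8.2 places LS children's ages at baseline, which suggests inclusion near the concealed period, and the protocol or the sampling procedure may settle it.
- **Motive.** A reader might infer that families in NutriVax wards would join the LS to obtain SQ-LNS. Section 1.5 describes mass supplementation at health centres, and nothing makes it conditional on joining the LS.
- **Adjustment already planned.** The re-run covers age, distance and several other covariates, so the age-mix illustration is addressed there. The gap is that the re-run is not the main analysis and names no prior dose.
- **Limits of prior dose.** Children under 9 months are expected to hold none, so it tells little about selection in that class. Willingness to consent stays unmeasured.
- **Power.** A reader might infer from the sample-size check that the LS has far too little power. The check concerns a binary comparison with a baseline measure, whereas the main analysis is now time-to-event. The present point does not rest on it.

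**Conclusion.** The concern holds in a limited form. Because the draw precedes enrolment and concealment is stated for one group only, arm differences among enrolled LS children may reflect selection as well as chance. The documents establish the possibility, not its occurrence. The firmer part is the model: the stated reason for omitting baseline status supports adjusting for age and prior dose jointly, and this would help whether an imbalance arose by selection or by chance.

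The illustrations span false differences of 1 to 8 points against the 10-point target, but every omission rate, uptake rate and age-specific incidence behind them is assumed. The point is confined to the LS, chiefly the main secondary endpoint. The anthropometric models already adjust for individual and ward baseline values.

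**What to change.** 1. **Section 3.4.2.2.** Put age class at inclusion (6 to under 9 months, 9 to 12 months) and card-recorded measles doses at inclusion (0, 1 or more, no card) in the main frailty Cox model, as covariates or as strata of the baseline hazard. Keep the unadjusted model as a sensitivity analysis and delete the sentence declining baseline adjustment.
2. **Section 3.3.** Limit the chance statement to ward characteristics fixed before the lottery, and say that arm differences among LS children may reflect enrolment selection.
3. **Reporting.** If refusals and exclusions were logged, tabulate them by arm and ward, with the discretionary criterion separate, as description only. Counting non-enrolled children as unvaccinated is not advised: the SAP mentions no refusal records, and children excluded under a criterion are not eligible.

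**Cost.** SAP wording and one model specification, to be settled before database lock and any comparative analysis. No new data are needed, since age, card and doses are already collected. The model gains two to three parameters if covariates are used. Its conditional HR will differ slightly from the unadjusted one, and the 12-month incidences must be averaged over the covariates. Only the measured part of any selection is removed.
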